3 STUDY DESIGN

3.1 Overall Design

This is a Phase 2, open-label, single-arm study evaluating the effect of ruxolitinib 1.5% cream on itch. This study will include approximately 48 adult participants (18-65 years old, inclusively) who have at least a 6-month history of AD and at least a 3-month history of chronic itch.

All participants will read and sign an Informed Consent Form (ICF) prior to any study procedures being performed and then undergo screening for study eligibility. Participants who meet initial screening requirements will be given access to an eDiary to complete the PP-NRS each morning (24-hour recall period), from screening to Day -1 and from Day 2 to the Day 29 visit. Participants must be willing and able to complete the eDiary on a daily basis for the duration of the study. During the last 7 days prior to Day 1 (run-in period; Day -7 to Day -1), participants will be required to complete at least 4 of 7 PP-NRS assessments in their eDiary. Inclusion of participants completing fewer than 4 of 7 PP-NRS questionnaires during the last 7 days of the screening period (run-in period) must be approved by the sponsor.

After a screening period of no more than 37 days (from Day -37 to Day -1, including a 7-day run-in period), participants who fulfill all of the inclusion criteria, none of the exclusion criteria, and have a baseline mean PP-NRS score ≥ 4.0 during the run-in period will be eligible to start the treatment period. The baseline mean PP-NRS score is defined as the average of all nonmissing PP-NRS scores reported during the run-in period.

During the treatment period, participants will have topical treatment with ruxolitinib 1.5% cream applied BID as a thin film for 28 (± 2) days (last application on the evening prior to the Day 29 visit). The study drug will be applied on all AD lesions, with a maximum treated area $\leq 20\%$ BSA. All original areas of involvement on Day 1 (even in the event of lesions clearing), and any new lesions (a maximum of $\leq 20\%$ BSA can be treated) must be treated until the evening prior to the Day 29 visit. On Day 1, participants will remain at the study center until after the 6-hour mPP-NRS assessment (approximately an 8-hour stay at the site). The 12-hour mPP-NRS assessment will be done at home just prior to the evening study drug application. On Day 8 and Day 15, the morning application of the study drug will be at the study center under the supervision of study staff. Other study drug applications will be self-administered by the participants at home. The study schema is shown in Figure 1 in the protocol.

Study drug application will occur in the morning and evening from Day 1 until the day prior to the Day 29 visit, with approximately 12 hours between applications. The evening dose should be applied at least 1 hour before bedtime. On Day 1, the mPP-NRS assessments should occur as close as possible to the scheduled time relative to the first study drug application. In addition, the 12-hour mPP-NRS should be completed before the evening study drug application. On Day 2, the PP-NRS assessment should be completed approximately 24 hours after the first study drug application and before the Day 2 morning dose. Refer to Table 5 for the sequence and timing of

	STATISTICAL ANALYSIS PLAN, Version Final v1.0
Protocol Number: INCB 18424-901	Sponsor: Incyte Corporation
Study Title: An Open-Label, Single-Arm Study to Evaluate the Effect of Ruxolitinib 1.5% Cream on Itch in Adult Participants With Atopic Dermatitis (SCRATCH-AD)	

these assessments and allowed windows on Day 1 and Day 2. From Day 3 until the Day 29 visit, the PP-NRS should be completed once daily, at approximately the same time in the morning, and prior to the study drug application.

Efficacy will be evaluated using the PP-NRS (worst itch over a 24-hour period), the mPP-NRS (current itch at the time of assessment), and the 5-point IGA.

The Body Surface Area (BSA) and Eczema Area and Severity Index (EASI) will be used to evaluate the participant's AD severity on Day 1 and will be characterized during the study.

Medical photographs of the target lesion(s) and application site adverse events (AEs) will be taken during the study. Participants will be asked to complete the Abbreviated 9-Item Treatment Satisfaction Questionnaire for Medication (TSQM-9) at the end of the treatment period (or ET, if applicable).

Safety will be assessed by collecting AEs, performing comprehensive and targeted physical examinations, and evaluating clinical laboratory assessments.

[figure not shown]

	STATISTICAL ANALYSIS PLAN, Version Final v1.0
Protocol Number: INCB 18424-901	Sponsor: Incyte Corporation
Study Title: An Open-Label, Single-Arm Study to Evaluate the Effect of Ruxolitinib 1.5% Cream on Itch in Adult Participants With Atopic Dermatitis (SCRATCH-AD)	

3.2 Schedule of Events

Table 3 of the protocol provides a description of the procedures planned at each visit.

Figure 1: Study Design Schema

3.3 Treatment

The treatment group is: ruxolitinib 1.5%, BID for 28 days.

3.4 Randomization, Replacement, and Unblinding Procedures

This is an open-label, single-arm study. No participants will be replaced at any time during this study.

3.5 Changes to the Analysis from the Protocol

No changes were made from the planned analysis in protocol.

4 POPULATIONS FOR ANALYSIS

4.1 Enrolled Analysis Set

The Enrolled analysis set will include all participants who sign the ICF.

	STATISTICAL ANALYSIS PLAN, Version Final v1.0
Protocol Number: INCB 18424-901	Sponsor: Incyte Corporation
Study Title: An Open-Label, Single-Arm Study to Evaluate the Effect of Ruxolitinib 1.5% Cream on Itch in Adult Participants With Atopic Dermatitis (SCRATCH-AD)	

4.2 Intent-to-Treat Analysis Set

The Intent-to-Treat (ITT) analysis set will include all enrolled participants who complete the run-in period (ie, not be a screen failed) and meet the inclusion and exclusion criteria. The ITT analysis set will be used for the summary of demographics, baseline characteristics, and participants disposition.

4.3 Modified Intent-to-Treat Analysis Set

The modified Intent-to-Treat (mITT) analysis set is a subset of the ITT analysis set, including participants who have both baseline and at least 1 post-baseline PP-NRS or mPP-NRS assessment within the treatment period. The mITT analysis set will be used for all efficacy analyses.

4.4 Per Protocol Analysis Set

The per protocol analysis set is a subset of the mITT analysis set, excluding participants with major protocol deviations that could potentially affect the efficacy evaluations. The per protocol analysis set will be used as supportive information for all efficacy analyses.

4.5 Safety Analysis Set

The Safety analysis set will include all enrolled participants who received at least 1 application of ruxolitinib 1.5% cream. All safety analyses will be conducted using the safety analysis set.

5 GENERAL CONSIDERATIONS

Formats and layouts of tables, listings, and figures (TLF) will be provided in a separate document (output general layout is described in [Appendix 1](#)).

5.1 Sample Size

Approximately 36 participants were planned to be enrolled into the study to receive ruxolitinib 1.5% cream. The sample size calculation was based on the CI for 1-sample mean. With an approximate 10% missing assessment rate at 24 hours, a sample size of 36 is required to produce a 2-sided 95% CI for the expected change from baseline in PP-NRS (24-hour recall period), with a precision of 0.57. The SD of 1.64 is estimated from 2 Phase 3, double-blind, randomized studies (INCB 18424-303 and INCB 18424-304). To ensure data quality and support study interpretation after deviations from protocol related to the timing of efficacy assessments were observed in the first participants enrolled, it was decided to enroll an additional 12 participants for a total of approximately 48 participants to be included.

	STATISTICAL ANALYSIS PLAN, Version Final v1.0
Protocol Number: INCB 18424-901	Sponsor: Incyte Corporation
Study Title: An Open-Label, Single-Arm Study to Evaluate the Effect of Ruxolitinib 1.5% Cream on Itch in Adult Participants With Atopic Dermatitis (SCRATCH-AD)	

5.2 Baseline

Unless otherwise specified, baseline value will be defined as the last non-missing assessment before or on Day 1 and prior to the first application of study drug (including unscheduled assessments). If the last non-missing assessment is performed on the same date as the first study treatment and time or timepoint is not available, the assessment will be considered as baseline, except for adverse events (AEs) and medications starting on the first study treatment dose date which will be considered post-baseline.

For PP-NRS, the baseline is defined as the average of all non-missing PP-NRS scores reported during the 7-day run-in period (Day -7 to Day -1).

5.3 Reference Start Date and Analysis Day

Analysis Day will be calculated from the first study treatment date and will be used to show start/end day of assessments or events.

Analysis day = (Date of event – Date of first dose administration) + 1 if date of event is on or after the date of first dose administration of study treatment;
 = (Date of event – Date of first dose administration) if date of event is before the date of first dose administration of study treatment.

In the situation where the assessment/event date is partial or missing, Analysis Day will be missing.

5.4 Windowing Conventions

No windowing conventions apply for this study.

5.5 Descriptive Statistics

All continuous variables will be summarized by presenting the number of participants, mean, standard deviation, standard error of the mean, median, minimum and maximum. Categorical variables will be presented as frequencies and percentages. Summary tables will be presented by visit, when applicable.

Change from baseline will be calculated as:

Assessment value at post-baseline visit X – Baseline value.

Percent change from baseline (%) will be calculated as:

(Assessment value at postbaseline visit X – Baseline value) / Baseline value * 100.

Percent change from baseline will be missing in situation where Baseline value equals to 0.

	STATISTICAL ANALYSIS PLAN, Version Final v1.0
Protocol Number: INCB 18424-901	Sponsor: Incyte Corporation
Study Title: An Open-Label, Single-Arm Study to Evaluate the Effect of Ruxolitinib 1.5% Cream on Itch in Adult Participants With Atopic Dermatitis (SCRATCH-AD)	

5.6 Statistical Tests

No formal statistical comparisons will be performed. Confidence intervals (CIs) will be two-sided with 95% coverage. Unless otherwise specified, confidence intervals for proportions will be calculated using the Clopper-Pearson method, as applicable.

5.7 Handling of Retests, Unscheduled Visits, and Early Termination Data

When retests measurements are done, the retest measurement will be considered for the summary analysis. All data from retest visits will be listed.

Unscheduled measurements will not be summarized in by-visit summary tables or figures. However, they will be included in shift summary tables. All data from unscheduled visits will be listed.

Early Termination visit assessments will be summarized as a separate visit in by-visit outputs. All data from early termination visits will be listed.

5.8 Software Version

All analyses will be performed using SAS® software Version 9.4 or higher.

6 STATISTICAL CONSIDERATIONS

6.1 Adjustments for Covariates

Not applicable.

6.2 Handling of Dropouts or Missing data

No imputation will be made for efficacy data. See [Appendix 2](#) for handling of completely or partially missing dates for prior and concomitant medications and adverse events.

6.3 Interim Analysis and Data Monitoring

No formal interim analysis is planned for this study.

6.4 Multicenter Studies

Not applicable.

	STATISTICAL ANALYSIS PLAN, Version Final v1.0
Protocol Number: INCB 18424-901	Sponsor: Incyte Corporation
Study Title: An Open-Label, Single-Arm Study to Evaluate the Effect of Ruxolitinib 1.5% Cream on Itch in Adult Participants With Atopic Dermatitis (SCRATCH-AD)	

6.5 Multiple Comparisons/Multiplicity

No adjustments for multiple comparison will be made for this study.

6.6 Examination of Subgroups

No subgroup analysis is planned for this study.

7 STUDY PARTICIPANTS

7.1 Disposition of Participants

All participants who provide informed consent will be accounted for in this study. The number of participants screened, rescreened, and who failed screening (screen failures) will be presented. The reason for screen failure will be presented for all screened participants who failed screening and rescreening, if applicable. The percentage of participants screen failures will be calculated using the number of participants screened as denominator. The percentage of reasons for screen failure will be calculated using the number of screen failures as denominator. The number of participants enrolled (who provide informed consent) and included in each analysis set will be presented and percentages will be based on the number of enrolled participants.

End of treatment status and treatment discontinuation related to COVID-19 or not will be presented. The percentage of end of treatment status will be calculated using the number of participants in the ITT analysis set. The percentage of treatment discontinuation related to COVID-19 or not will be calculated using the number of participants in the ITT analysis set who did not complete the treatment. Study completion status and the reason for study discontinuation will also be presented, including discontinuation related to COVID-19. The percentage of reasons for study discontinuation will be calculated using the number of participants in the ITT analysis set who did not complete study as denominator (and related or not to COVID-19, if applicable). Otherwise, the percentages will be calculated using the number of participants included in the ITT analysis set as denominator.

Number of days in the study will be calculated as follows and summarized:

$$\text{Number of days in study} = \text{Date of completion/discontinuation} - 1^{\text{st}} \text{ dose date} + 1.$$

If a participant had no dose, the number of days in the study will be left as missing. A listing of participants' disposition and a listing of participants included in each of the analysis sets will also be provided based on the Enrolled analysis set. Information on first screening for participants who were rescreened, including the rescreened participant identifier, will be presented under the first screening participant identifier.

	STATISTICAL ANALYSIS PLAN, Version Final v1.0
Protocol Number: INCB 18424-901	Sponsor: Incyte Corporation
Study Title: An Open-Label, Single-Arm Study to Evaluate the Effect of Ruxolitinib 1.5% Cream on Itch in Adult Participants With Atopic Dermatitis (SCRATCH-AD)	

7.2 Protocol Deviations

Protocol deviations will be classified as major or minor prior to database lock.

The number of participants with at least one major protocol deviation will be summarized by deviation category on the safety analysis set. Important protocol deviations will be summarized in a similar way. A listing of all protocol deviations will also be provided.

The number of events and the number and percentage of participants with at least one protocol deviation associated with COVID-19 will be summarized by deviation category using the safety analysis set. A listing of all protocol deviations associated with COVID-19 will also be provided.

8 DEMOGRAPHIC AND OTHER BASELINE CHARACTERISTICS

Demographics and baseline characteristics will be summarized with descriptive statistics based on the ITT analysis set and on the per protocol analysis set. The list of demographics and baseline characteristics to be summarized will include:

- Age (years) – as recorded in the CRF
- Sex at birth
- Ethnicity (Hispanic or Latino, Not Hispanic or Latino, Unknown)
- Race* (White, American Indian or Alaska native, Asian, Native Hawaiian or other Pacific islander, Black or African American, Unknown)
- Baseline Height (cm)
- Baseline Weight (kg)
- Fitzpatrick skin type
- Baseline Body Surface Area for eligibility (%) (excluding palms, soles, scalp, genitals, and folds)
- Baseline Total Body Surface Area affected (%)
- Baseline Body Surface Area treated (%)
- Baseline Peak-Pruritus Numerical Rating Scale (run-in period mean score)
- Baseline Modified Peak-Pruritus Numerical Rating Scale

	STATISTICAL ANALYSIS PLAN, Version Final v1.0
Protocol Number: INCB 18424-901	Sponsor: Incyte Corporation
Study Title: An Open-Label, Single-Arm Study to Evaluate the Effect of Ruxolitinib 1.5% Cream on Itch in Adult Participants With Atopic Dermatitis (SCRATCH-AD)	

- Baseline Investigator Global Assessment
- Baseline Eczema Area and Severity Index
- Baseline Transepidermal Water Loss (TEWL) (lesional and non-lesional)

*Participants who reported more than one race will be summarized as 'Multiple' race in the table. All races selected will be displayed in the listing.

A listing of all demographics and baseline characteristics will be provided for the ITT analysis set.

9 SURGICAL AND MEDICAL HISTORY

Medical history will be coded according to the Medical Dictionary for Regulatory Activities (MedDRA), Version 24.0.

General surgical and medical history will be summarized by system organ class (SOC) and preferred term (PT) on the safety analysis set. A participant who experienced the same surgical and medical history event multiple times will be counted only once for the corresponding PT. Similarly, if a participant experienced multiple surgical and medical history events within the same SOC, the participant will be counted only once for that SOC. Surgical and medical history events will be sorted alphabetically by SOC and within each SOC the PT will be presented by decreasing order.

A listing of all general surgical and medical history events will be provided.

Disease-targeted Atopic Dermatitis (AD) medical history will be summarized based on the safety analysis set. Disease duration, chronic itch (yes/no), prior history of asthma (yes/no), prior allergies (yes/no), history of contact dermatitis (yes/no), common complications associated, time from onset, presence of head and neck, facial and periorbital involvement (yes/no), and the number of AD episodes/flare-ups over the last 12 months will be reported.

The disease duration (in years) will be calculated as follow:

Disease duration = (Date of first dose of study treatment – Date of initial AD diagnostic)/365.25.

The time from onset (in years) will be calculated as follow:

Time from onset = (Date of first dose of study treatment – Current date of onset of AD episode)/365.25.

Completely or partially missing dates for the date of AD diagnostic and the current date of onset of AD will be imputed as follow:

	STATISTICAL ANALYSIS PLAN, Version Final v1.0
Protocol Number: INCB 18424-901	Sponsor: Incyte Corporation
Study Title: An Open-Label, Single-Arm Study to Evaluate the Effect of Ruxolitinib 1.5% Cream on Itch in Adult Participants With Atopic Dermatitis (SCRATCH-AD)	

- Completely missing: Leave missing.
- Missing day and month: Impute to January 1st.
- Missing day: Impute to the 1st of the month.

A listing of all disease-specific AD history, including date of AD diagnostic and date of current onset, will be provided.

10 PRIOR AND CONCOMITANT MEDICATIONS AND THERAPIES

10.1 Prior and Concomitant Medications

Medications will be coded according to the World Health Organization Drug Dictionary (WHO-DD), B3 March 2021.

Prior medications are defined as any medication started and discontinued prior to the first study treatment dose. Concomitant medications are defined as any medication taken after the first study treatment dose, including those who started prior to the first study treatment date and continued past that date. See [Appendix 2](#) for handling of completely or partially missing dates for prior and concomitant medications.

Incidence of prior and concomitant medications will be tabulated separately by ATC level 3 and PT on the safety analysis set. A participant with the same medication taken multiple times will be counted only once for the corresponding PT. Similarly, if a participant has taken more than one medication within the same ATC level, then the participant will be counted only once for that ATC. A listing of all prior and concomitant medications will be provided.

All disease-specific (AD) prior medications and therapies will be tabulated separately in a similar way and based on the safety analysis set. Additionally, a listing of all prior medications and therapies related to AD will be provided.

10.2 Non-drug Therapies and Surgical Procedures

Non-drug therapies and surgical procedures will be coded according to the Medical Dictionary for Regulatory Activities (MedDRA), Version 24.0.

Prior non-drug therapies and surgical procedures are defined as any non-drug therapy and surgical procedure started and discontinued prior to the first study treatment dose. Concomitant non-drug therapies and surgical procedures are defined as any non-drug therapy and surgical procedure taken after the first study treatment dose, including those who started prior to the first study treatment date and continued past that date. See [Appendix 2](#) for handling of completely or partially missing dates for non-drug therapies and surgical procedures.

	STATISTICAL ANALYSIS PLAN, Version Final v1.0
Protocol Number: INCB 18424-901	Sponsor: Incyte Corporation
Study Title: An Open-Label, Single-Arm Study to Evaluate the Effect of Ruxolitinib 1.5% Cream on Itch in Adult Participants With Atopic Dermatitis (SCRATCH-AD)	

Incidence of prior and concomitant non-drug therapies and surgical procedures will be tabulated separately by system organ class (SOC) and preferred term (PT) on the safety analysis set. A participant who experienced the same non-drug therapies and surgical procedures event multiple times will be counted only once for the corresponding PT. Similarly, if a participant experienced multiple non-drug therapies and surgical procedures events within the same SOC, the participant will be counted only once for that SOC. Non-drug therapies and surgical procedures will be sorted alphabetically by SOC and within each SOC the PT will be presented by decreasing order.

A listing of all non-drug therapies and surgical procedures will be provided.

11 STUDY TREATMENT EXPOSURE AND TREATMENT COMPLIANCE

Duration of exposure to study treatment, in days, will be computed as follows:

$$\text{Duration of exposure} = [(\text{Date of last dose of study treatment} - \text{Date of first dose of study treatment}) + 1]$$

Compliance with study treatment (%) will be calculated as follows:

$$\frac{\text{Number of applications per participant eDiary}}{\text{Total number of intended applications}} \times 100$$

For each participant, the total number of intended applications corresponds to 2 applications per day from the day of first dose until the end of treatment date:

$$\text{Total number of intended applications} = [(\text{Date of end of treatment} - \text{Date of first dose of study treatment}) + 1] \times 2.$$

Descriptive statistics for the duration of exposure, number of applications (based on the participant's eDiary) and compliance to study treatment will be presented based on the safety analysis set. Frequency distribution will also be presented for the following compliance categories: <80% , 80% to 120%, >120%.

A summary of cumulative dose applied will be presented based on the safety analysis set. Cumulative dose will be derived based on the information on the dispensed tubes weight and returned tubes weight captured in the drug accountability form. Cumulative dose (in grams) will be computed as follow:

$$(\text{Sum of tubes weight dispensed} - \text{Sum of tubes weight returned}).$$

	STATISTICAL ANALYSIS PLAN, Version Final v1.0
Protocol Number: INCB 18424-901	Sponsor: Incyte Corporation
Study Title: An Open-Label, Single-Arm Study to Evaluate the Effect of Ruxolitinib 1.5% Cream on Itch in Adult Participants With Atopic Dermatitis (SCRATCH-AD)	

If the information on tube weight is missing (i.e. tube not returned), cumulative dose will be missing.

A listing of exposure, compliance, study treatment administrations, treatment interruptions and study treatment accountability will be provided.

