8.1.4. Diaries

At the screening visit, participant email addresses will be collected and used for log-in access to an eDiary (tablet). Participants will be trained to complete the eDiary once daily, starting from screening and up to the Day 29 visit, and will receive daily email reminders for completion. The eDiary will capture the daily PP-NRS assessment starting at screening up to the Day 29 visit with the exception of Day 1.

A paper diary will also be provided to participants to capture the date and time of twice daily study drug applications starting at the Day 1 visit.

Participants may be contacted on Day 1 and Day 2 as a reminder to complete their dairies.

The completed diaries will be reviewed during each study visit, and data will be confirmed by the study staff. Qualified clinical staff will review the participants' entries for compliance.

Participants will be considered compliant with the treatment regimen if they apply at least 80% but no more than 120% of the expected number of applications during participation in the treatment period of the study. Participants who are noncompliant will have their administration instructions reinforced by the investigator or a qualified designee.

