1 INTRODUCTION

This Statistical Analysis Plan (SAP) describes the planned analysis and reporting for Incyte Corporation clinical protocol INCB 18424-901. The analyses described in the SAP are based upon the protocol version Amendment 3 dated 09-MAY-2022.

This SAP has been developed prior to database lock and final analyses. All final analyses will be performed after the clinical trial data are entered into the database, any discrepancies in the data are resolved, the lock of the database, and following the signature of the SAP.

--	--

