12.1 Primary Endpoint

12.1.1 Peak-Pruritus Numerical Rating Scale

The intensity of pruritus (itch) will be recorded daily in the eDiary from the screening visit until Day -1 and from Day 2 to the Day 29 visit, using the Peak-Pruritus Numerical Rating Scale (PP-NRS) (24-hour recall period). This NRS will be evaluated by asking participants to assign a numerical score representing their itch at the worst moment during the previous 24 hours on a scale of 0 to 10, with 0 being no itch and 10 being the worst itch imaginable.

The PP-NRS will be analyzed as follow:

- Change from baseline in PP-NRS at Day 2 (24-hour recall period after first application).

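### SAP section 11 takes the number of applications and the compliance numerator from the eDiary, but the protocol version it is based on records applications in the paper diary

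*SAP*

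**What the plan says.** SAP section 11 computes compliance as a percentage. The numerator is "Number of applications per participant eDiary" and the denominator is the total number of intended applications, defined as "2 applications per day from the day of first dose until the end of treatment date". The same section summarises the "number of applications (based on the participant's eDiary") on the safety set, and tabulates compliance as <80%, 80% to 120% and >120%. The eDiary is named for every participant, without exception.

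On its relation to the protocol, SAP section 1 says: "The analyses described in the SAP are based upon the protocol version Amendment 3 dated 09-MAY-2022". SAP section 3.5 adds: "No changes were made from the planned analysis in protocol".

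The protocol assigns the two diaries different jobs. Protocol section 8.1.4 says of the electronic one: "The eDiary will capture the daily PP-NRS assessment starting at screening up to the Day 29 visit with the exception of Day 1". Of the other it says: "A paper diary will also be provided to participants to capture the date and time of twice daily study drug applications". Protocol Table 3, section 4.1.1 and section 6.4 also put study drug applications in the paper diary.

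**The concern.** Compliance here is a count of recorded applications divided by a count of intended ones, so the numerator is only as good as the record it is taken from. If the SAP directs the programmer to an instrument that was not meant to hold application records, the rule either cannot be executed or returns an incomplete count.

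Two planned outputs depend on it: the number of applications, which protocol section 10.4.4 gives as an example of an exposure measure, and the compliance percentage with its three categories. The 80% to 120% range is also the protocol's own definition of a compliant participant (sections 6.4 and 8.1.4), so this table is where the report would show whether participants met it.

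There is a procedural cost as well. If the team does the sensible thing and uses the paper diary, it departs from SAP section 11 as written, and protocol section 10.4.1 asks for deviations from the SAP to be described and justified in the final report.

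**Working it through.** The plan states no figure that depends on the source, so the check is a comparison of texts.

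1. **What the SAP formula needs.** Compliance (%) = applications recorded ÷ intended applications × 100, with intended applications = [(end of treatment date − first dose date) + 1] × 2. For 28 treatment days the denominator is 28 × 2 = 56. It comes from dates, not from a diary, and is not in dispute. Only the numerator depends on the diary.

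2. **Where the SAP looks for the numerator.** The eDiary, named twice in section 11.

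3. **Where the Amendment 3 protocol puts application records.**
   - Table 3: the note for the paper diary assigns it study drug application; the note for the eDiary assigns it the PP-NRS.
   - Section 4.1.1 (COVID-19 conduct): PP-NRS by eDiary on the tablet, twice-daily applications in the paper diary.
   - Section 6.4: a paper diary is supplied for the time and date of each application.
   - Section 8.1.4: the eDiary takes the daily PP-NRS; the paper diary takes the applications.

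   No current section of the protocol assigns application records to the eDiary.

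4. **Whether eDiary is loose wording for either diary.** It is not. SAP section 12.1.1 uses the term for the PP-NRS instrument: "The intensity of pruritus (itch) will be recorded daily in the eDiary from the screening visit until Day -1". SAP section 3.1 uses it the same way. Protocol Table 3 treats the paper diary and the tablet eDiary as two separate items, both brought to each visit for review. The SAP text available never mentions a paper diary.

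5. **Whether the amendment history changes the answer.** The conflict is between current SAP text and current protocol text, so it does not rest on the amendment log. The log only offers a likely origin: the Amendment 2 summary in protocol Appendix E describes an eDiary that would capture applications, and Amendment 3 moved them to paper. The rationale given for Amendment 3 is that the eDiary does not collect the time of applications. That leaves open whether it held any application counts for participants already enrolled.

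6. **What depends on the named source.** In SAP section 11, duration of exposure uses first and last dose dates, and cumulative dose uses dispensed and returned tube weights. Neither uses diary counts. The Day 2 primary endpoint is a PP-NRS score, for which the eDiary is the correct source. That leaves the number of applications and the compliance percentage.

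**The case against.** The strongest reply is that this is a label and would correct itself. SAP section 11 also plans a listing of study treatment administrations, so application-level data are evidently expected in the analysis database. A programmer who found no application fields in the eDiary data would raise a query, not publish an empty table. This is fair as a forecast, and it is why the point is minor. It does not make the written rule right: section 11 names a specific instrument twice, and nothing else in the SAP redirects the reader.

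It can also be said that SAP section 3.5 concerns only the planned analysis, and that protocol section 10.4.4 names no source for the number of applications. That stands. The conflict is with the data-capture text in protocol Table 3 and sections 4.1.1, 6.4 and 8.1.4, not with section 10.4.4.

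A reader might infer more than the documents support, in five ways:

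- **That adherent participants would be scored as 0% compliant.** An instrument with no application field gives no numerator, not a zero. Missing is the likelier result.
- **That a share of the 48 participants affected can be calculated from the 12 added under Amendment 3.** The documents do not report how many were enrolled before the amendment, or what those participants' eDiaries held. Neither a lower nor an upper bound can be set.
- **That interruption days are left undefined.** They are not. The denominator is elapsed days × 2 with no deduction, so those days count as intended applications, and interruptions are listed separately.
- **That the denominator is inflated by running to the Day 29 visit.** SAP sections 3.1 and 3.3 end application the evening before that visit, after 28 days. For early discontinuation, protocol section 7.1.2 has the last application date recorded in the eCRF. Naming the date variable would be a refinement; its absence is not an error.
- **That the per protocol set is affected.** No text links this percentage to it. It excludes major deviations that could affect efficacy, and the documents do not say whether low compliance is one.

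**Conclusion.** The point holds. SAP section 11 names, for every participant, a source to which the protocol version it is based on assigns no application records. Followed literally, the number of applications and the compliance percentage would be missing or wrong for anyone whose applications are only on paper. The number of such participants is unknown.

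The consequence is small. Both outputs are descriptive summaries on the safety set, and no estimate or confidence interval for efficacy depends on them. The conclusion assumes that applications were in fact recorded as the current protocol directs. For participants enrolled before Amendment 3 the documents do not confirm this.

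**What to change.** In SAP section 11, replace eDiary in both places (the compliance numerator and the number-of-applications summary) with the paper diary, or better with the eCRF data or dataset derived from it. The documents do not say how paper entries reach the database: protocol Table 3 says only that sites copy the paper diary before returning it. Naming the dataset would close that gap as well.

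If any participant enrolled before Amendment 3 has applications recorded only in the eDiary, add one sentence naming the source used for them.

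The cost is a change of source name in two places and, if needed, one sentence. The formula, the denominator and the compliance categories stay as they are. Because the current protocol already provides for the paper diary, no new data collection is required. Making the change before database lock avoids having to report a departure from the SAP later.
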